## 8.2 Neoadjuvant Dose Modifications Based on Adverse Events

If all study medications are discontinued or all study medications are omitted for more than 28 days due to adverse events during the neoadjuvant period, the patient should proceed to surgery (once stable).

The days on which doses are omitted are not to be made up. For example, if vemurafenib is omitted on Days 1-3 of a cycle with recovery to Grade  $\leq 1$  on Day 4 of that cycle, the patient will receive vemurafenib on only Days 4-21 of the cycle.

If all study medications are discontinued due to adverse events during the adjuvant period, the patient should proceed to observation.

Providers may hold, delay, or reduce (in line with Section 8.1) doses, even in the absence of a requirement to do so in this table (Section 8.2) per clinical judgement to maximize patient safety. For example, if the patient's AE is Grade 2, and the table does not indicate a change in action, if the provider determines that the patient's Grade 2 AE is severe enough to warrant a change in the patient's clinical care (i.e., for medically significant or intolerable Grade 2 AE despite appropriate (maximal) supportive care), then the provider may make that change, as long as the reason for the change is discussed with the PI, and documented in the medical record.

### 8.21 Table for Arms A and B only

CTCAE System/Organ/Class (SOC)	ADVERSE EVENTS/SYMPTOMS	ACTIONS		
		Vemurafenib (BRAF-mutant only)	Cobimetinib	Atezolizumab (All patients)
Cardiac Disorders	Heart failure OR Left ventricular systolic dysfunction Clinically asymptomatic LVEF <40% or 40-49% and >10% decrease from baseline	Continue	Omit x 2 weeks repeat LVEF assessment If LVEF > LLN and absolute LVEF <10% decrease from baseline – resume with dose reduced -1 dose level If LVEF < LLN or $\geq 10\%$ decrease from baseline, discontinue	Continue

CTCAE System/Organ/Class (SOC)	ADVERSE EVENTS/SYMPTOMS	ACTIONS		
		Vemurafenib (BRAF-mutant only)	Cobimetinib	Atezolizumab (All patients)
Cardiac Disorders	Clinically symptomatic	Continue	Omit x 4 weeks repeat LVEF assessment If asymptomatic after 4 weeks and repeat LVEF shows >LLN and <10% decrease from baseline, resume with dose reduced -1 dose level If LVEF <LLN or ≥10% decrease from baseline, discontinue.	Omit until myocarditis is ruled out by Cardiology
Endocrine disorders	Adrenal insufficiency Grade ≥2	Continue	Continue	Omit until improves to ≤Grade 1 Discontinue if not improved within 12 weeks Refer to endocrinologist
Endocrine disorders	Hyperglycemia Grade 3-4	Continue	Continue	Omit and initiate treatment under endocrinologist care Resume when symptoms resolve and glucose levels are stable
Endocrine disorders	Hyperthyroidism Grade ≥2 or TSH < 0.1 mU/L	Continue	Continue	Omit and initiate therapy under endocrinologist care Resume when symptoms resolve to ≤Grade 1 Refer to Endocrinology
Endocrine disorders	Endocrine disorders, other specify Symptomatic Hypophysitis	Continue	Continue	Omit and refer to endocrinologist Resume when symptoms resolve to ≤Grade 1
Eye disorders (refer to Ophthalmology)	Blurred vision or Eye pain or Uveitis or Eye disorders-other specify: iritis (immune-related) Grade 2	Continue	Continue	Omit Resume when symptoms resolve to ≤Grade 1

CTCAE System/Organ/Class (SOC)	ADVERSE EVENTS/SYMPTOMS	ACTIONS		
		Vemurafenib (BRAF-mutant only)	Cobimetinib	Atezolizumab (All patients)
Eye disorders (refer to Ophthalmology)	Grade $\geq 3$	Omit until $\leq$ Grade 1 Resume with dose reduced by 1 level once $\leq$ Grade 1	Omit until $\leq$ Grade 1 Resume at same dose once $\leq$ Grade 1	Discontinue
	Retinopathy (serous retinopathy, chorioretinopathy) or Retinal detachment (RPED) Grade 2-3	Omit until $\leq$ Grade 1 Resume at same dose once $\leq$ Grade 1	Omit until $\leq$ Grade 1 Resume at dose reduced by 1 level once $\leq$ Grade 1	Continue
	Grade 4	Omit until $\leq$ Grade 1 Resume with dose reduced by 1 level once $\leq$ Grade 1	Discontinue	Continue
Eye disorders (refer to Ophthalmology)	Retinal vascular disorder (Retinal Vein Occlusion) (Any grade)	Discontinue	Discontinue	Continue
Gastrointestinal disorders	Diarrhea/Colitis Grade 2	Omit until symptoms resolve to $\leq$ Grade 1 For Grade 2 may resume previous dose level	Omit until symptoms resolve to $\leq$ Grade 1 Resume at one dose level lower	Omit and resume when symptoms resolve to $\leq$ Grade 1,
	Grade 3	Omit until symptoms resolve to $\leq$ Grade 1 Resume at one dose level lower	Omit until symptoms resolve to $\leq$ Grade 1 Resume at one dose level lower	Omit and resume when symptoms resolve to $\leq$ Grade 1
	Grade 4	Discontinue	Discontinue	Discontinue
	Pancreatitis (amylase/lipase increased) Grade 2	Continue	Continue	Continue at provider's discretion Monitor amylase/lipase weekly See Section 9.0
	Grade 3	Omit until $\leq$ Grade 2 Resume with dose reduced by 1 levels once $\leq$ Grade 2	Omit until $\leq$ Grade 2 Resume with dose reduced by 1 levels once $\leq$ Grade 2	Omit until $\leq$ Grade 2 Initiate supportive care per Section 9.0 Resume once symptoms resolve to $\leq$ Grade 2 If pancreatitis recurs, permanently discontinue atezolizumab

CTCAE System/Organ/Class (SOC)	ADVERSE EVENTS/SYMPTOMS	ACTIONS		
		Vemurafenib (BRAF-mutant only)	Cobimetinib	Atezolizumab (All patients)
	Grade 4	Omit until $\leq$ Grade 2 Resume with dose reduced by 1 levels once $\leq$ Grade 2	Omit until $\leq$ Grade 2 Resume with dose reduced by 1 levels once $\leq$ Grade 2	Discontinue
General disorders and administration site conditions	Infusion-related reaction Grade $\geq 3$	Continue	BRAFm – Continue BRAFWt – Discontinue	Discontinue
Immune System Disorders	Allergic reaction or Anaphylaxis Grade 2	Continue	Continue	Omit and resume when symptoms resolve to $\leq$ Grade 1 Pre-treatment required prior to subsequent doses Resume at same dose
	Grade $\geq 3$	Discontinue	Discontinue	Discontinue
Immune System Disorders	Immune System Disorders, Other: Immune-related myasthenic syndrome/myasthenia gravis, Guillain-Barré or meningoencephalitis	Continue	Continue	Permanently discontinue atezolizumab
Investigations	Aspartate aminotransferase or Alanine aminotransferase increased Grade 1	Continue, but monitor LFTs weekly	Continue, but monitor LFTs weekly	Continue, but monitor LFTs weekly
	Grade 2 (AST/ALT $>3.0$ - $5.0$ x ULN)	Omit treatment Monitor LFTs weekly Resume with dose reduced by 1 level once $\leq$ Grade 1	Omit treatment Monitor LFTs weekly Resume at previous dose level once $\leq$ Grade 1	Omit treatment Monitor LFTs weekly Resume when symptoms resolve to $\leq$ Grade 1
	Grade 3 (AST/ALT $>5.0$ - $10.0$ x ULN)	Omit until $\leq$ Grade 1 Resume with dose reduced by 2 levels once $\leq$ Grade 1	Omit until $\leq$ Grade 1 Resume with dose reduced by 2 levels once $\leq$ Grade 1	Omit and initiate systemic steroid treatment (see Section 9.0) Consult Hepatology if not improving within 1 week Resume when symptoms resolve to $\leq$ Grade 1
	Grade 3+ (AST/ALT $>10.0$ x ULN)	Discontinue	Discontinue	Discontinue Consult Hepatology
	Blood bilirubin increased Total bilirubin $\leq 2$ x ULN	Continue	Continue	Continue

CTCAE System/Organ/Class (SOC)	ADVERSE EVENTS/SYMPTOMS	ACTIONS		
		Vemurafenib (BRAF-mutant only)	Cobimetinib	Atezolizumab (All patients)
Investigations	Total bilirubin >2 x ULN For patients with Gilbert's syndrome: modify dose only if direct bilirubin is >2 x ULN	Discontinue	Discontinue	Discontinue Consult Hepatology
	CPK increased Symptomatic (Any grade) or rhabdomyolysis	Continue	Omit until ≤Grade 1 Resume at dose reduced one level once ≤Grade 1	Continue
	Electrocardiogram QT corrected interval prolonged >500 ms (≥Grade 3) and change from baseline ≤60 ms OR ≤500 ms and change from baseline >60 ms	Omit until ≤500 ms and change from baseline ≤60 ms When recovered, resume with dose reduced by 1 level	Continue	Continue
Investigations	Electrocardiogram QT corrected interval prolonged >500 ms and change from baseline >60 ms	Discontinue vemurafenib	Continue	Continue
Nervous system disorders	Intracranial hemorrhage Any grade	Omit and discontinue if not resolved within 28 days	Discontinue	Continue
Renal and urinary disorders	Acute kidney injury Grade 2	Continue	Continue	Omit until ≤Grade 1 Resume when symptoms resolve to ≤Grade 1
Renal and urinary disorders	Grade ≥3	Omit until ≤Grade 1 Resume at same dose once ≤Grade 1	BRAFm: Omit until ≤Grade 1 Resume at same dose once ≤Grade 1 BRAFWt: Discontinue	Discontinue
Respiratory, thoracic and mediastinal disorders	Pneumonitis Grade 2	Omit until ≤Grade 1 Resume at same dose once ≤Grade 1	Omit until ≤Grade 1 Resume at same dose once ≤Grade 1	Omit until ≤Grade 1 Resume once symptoms resolve to ≤Grade 1
	Grade ≥3	Omit until ≤Grade 1 Resume with dose reduced by 1 level once ≤Grade 1	Discontinue	Discontinue

CTCAE System/Organ/Class (SOC)	ADVERSE EVENTS/SYMPTOMS	ACTIONS		
		Vemurafenib (BRAF-mutant only)	Cobimetinib	Atezolizumab (All patients)
Skin and subcutaneous tissue disorders	Photosensitivity Grade 2 lasting >7 days	Omit until $\leq$ Grade 1 Resume with dose reduced by 1 level once $\leq$ Grade 1 If event does not resolve within 28 days, discontinue	Omit until $\leq$ Grade 1 Resume at current dose once $\leq$ Grade 1 If event does not resolve within 28 days, discontinue	Continue
	Grade 3-4	Omit until $\leq$ Grade 1 Resume with dose reduced by one dose level If event does not resolve within 28 days, discontinue	Omit until $\leq$ Grade 1 Resume at current dose level If event does not resolve within 28 days, discontinue	Continue
Skin and subcutaneous tissue disorders	Rash acneiform Grade 2	Continue	Continue	Continue Initiate supportive care per Section 9.0 Refer to Dermatology if does not improve to $\leq$ Grade 1 within 2 weeks
	Grade 3	Continue	Omit until $\leq$ Grade 1 Resume with dose reduced by 1 level once $\leq$ Grade 1	Omit and initiate supportive care per Section 9.0 Refer to Dermatology Resume once $\leq$ Grade 1
	Grade 4	Discontinue	Discontinue	Omit and initiate supportive care per Section 9.0 Refer to Dermatology Resume once $\leq$ Grade 1
	Rash maculo-papular Grade 2	Continue (See Section 9.0)	Continue	Continue Initiate supportive care per Section 9.0 Refer to Dermatology if does not improve to $\leq$ Grade 1 within 2 weeks

CTCAE System/Organ/Class (SOC)	ADVERSE EVENTS/SYMPTOMS	ACTIONS		
		Vemurafenib (BRAF-mutant only)	Cobimetinib	Atezolizumab (All patients)
	Grade 3	Omit until $\leq$ Grade 1 Resume with dose reduced by 1 level once $\leq$ Grade 1	Continue	Omit and initiate supportive care per Section 9.0 Refer to Dermatology Resume when symptoms resolve to $\leq$ Grade 1
	Grade 4	Discontinue	Discontinue	Discontinue
Other Adverse Events	Grade 3	Omit until $\leq$ Grade 1 Resume with dose reduced by 1 level once $\leq$ Grade 1	Omit until $\leq$ Grade 1 Resume with dose reduced by 1 level once $\leq$ Grade 1	Omit until $\leq$ Grade 1 Resume once symptoms resolve to $\leq$ Grade 1
	Grade 4	Discontinue	Discontinue	Discontinue

#### 8.22 Table for Arm C only: Atezolizumab and Tiragolumab

If either study drug is delayed for a related toxicity, it is recommended that the other study drug is also delayed since the safety profiles for atezolizumab and tiragolumab are similar.

In case of delays in dosing of one study drug for drug-related toxicity while the other study drug is given as planned, it is recommended that the study drug being delayed will be administered at the next scheduled infusion (i.e., at the next scheduled 21-day cycle).

CTCAE System/Organ/Class (SOC)	ADVERSE EVENTS/SYMPTOMS	ACTIONS	
		Tiragolumab	Atezolizumab
Cardiac Disorders	Any which are clinically symptomatic	Omit until myocarditis is ruled out by Cardiology	Omit until myocarditis is ruled out by Cardiology
Endocrine disorders	Adrenal insufficiency Grade $\geq 2$	Omit until improves to $\leq$ Grade 1 Discontinue if not improved within 12 weeks Refer to endocrinologist	Omit until improves to $\leq$ Grade 1 Discontinue if not improved within 12 weeks Refer to endocrinologist
Endocrine disorders	Hyperglycemia Grade 3-4	Omit and initiate treatment under endocrinologist care Resume when symptoms resolve and glucose levels are stable	Omit and initiate treatment under endocrinologist care Resume when symptoms resolve and glucose levels are stable
Endocrine disorders	Hyperthyroidism Grade $\geq 2$ or TSH $< 0.1$ mU/L	Omit and initiate therapy under endocrinologist care Resume when symptoms resolve to $\leq$ Grade 1 Refer to Endocrinology	Omit and initiate therapy under endocrinologist care Resume when symptoms resolve to $\leq$ Grade 1 Refer to Endocrinology

CTCAE System/Organ/Class (SOC)	ADVERSE EVENTS/SYMPTOMS	ACTIONS	
		Tiragolumab	Atezolizumab
Endocrine disorders	Endocrine disorders, other specify Symptomatic Hypophysitis	Omit and refer to endocrinologist Resume when symptoms resolve to $\leq$ Grade 1	Omit and refer to endocrinologist Resume when symptoms resolve to $\leq$ Grade 1
Eye disorders (refer to Ophthalmology)	Blurred vision or Eye pain or Uveitis or Eye disorders-other specify: iritis (immune-related) Grade 2	Omit Resume when symptoms resolve to $\leq$ Grade 1	Omit Resume when symptoms resolve to $\leq$ Grade 1
	Grade $\geq 3$	Omit until $\leq$ Grade 1	Discontinue
Gastrointestinal disorders	Diarrhea/Colitis Grade 2	Omit and resume when symptoms resolve to $\leq$ Grade 1	Omit and resume when symptoms resolve to $\leq$ Grade 1
	Grade 3	Omit and resume when symptoms resolve to $\leq$ Grade 1	Omit and resume when symptoms resolve to $\leq$ Grade 1
Gastrointestinal disorders	Grade 4	Discontinue	Discontinue
	Pancreatitis (amylase/lipase increased) Grade 2	Continue at provider's discretion Monitor amylase/lipase weekly See Section 9.0	Continue at provider's discretion Monitor amylase/lipase weekly See Section 9.0
	Grade 3	Omit until $\leq$ Grade 2 Initiate supportive care per Section 9.0 Resume once symptoms resolve to $\leq$ Grade 2 If pancreatitis recurs, permanently discontinue	Omit until $\leq$ Grade 2 Initiate supportive care per Section 9.0 Resume once symptoms resolve to $\leq$ Grade 2 If pancreatitis recurs, permanently discontinue atezolizumab
	Grade 4	Discontinue	Discontinue
General disorders and administration site conditions	Infusion-related reaction Grade $\geq 3$	Discontinue See Section 9.0	Discontinue See Section 9.0
Immune system disorders	Allergic reaction or Anaphylaxis Grade 2	Omit and resume when symptoms resolve to $\leq$ Grade 1 Pre-treatment required prior to subsequent doses Resume at same dose	Omit and resume when symptoms resolve to $\leq$ Grade 1 Pre-treatment required prior to subsequent doses Resume at same dose
	Grade $\geq 3$	Discontinue	Discontinue

CTCAE System/Organ/Class (SOC)	ADVERSE EVENTS/SYMPTOMS	ACTIONS	
		Tiragolumab	Atezolizumab
Immune system disorders	Cytokine release syndrome Grade $\geq 3$ per CTCAE v 5.0	Discontinue if CRS due to tiragolumab See Section 9.7	Discontinue if CRS due to atezolizumab See Section 9.7
Immune system disorders	Immune System Disorders, Other: Hemophagocytic lymphohistiocytosis (HLH) and macrophage activation syndrome (MAS)	Discontinue See Section 9.0	Discontinue See Section 9.0
Immune system disorders	Immune System Disorders, Other: Immune-related myasthenic syndrome/myasthenia gravis, Guillain-Barré or meningoencephalitis	Permanently discontinue tiragolumab	Permanently discontinue atezolizumab
Investigations	Aspartate aminotransferase or Alanine aminotransferase increased Grade 1	Continue, but monitor LFTs weekly	Continue, but monitor LFTs weekly
	Grade 2 (AST/ALT $>3.0$ - $5.0$ x ULN)	Omit treatment Monitor LFTs weekly Resume when symptoms resolve to $\leq$ Grade 1	Omit treatment Monitor LFTs weekly Resume when symptoms resolve to $\leq$ Grade 1
	Grade 3 (AST/ALT $>5.0$ - $10.0$ x ULN)	Omit and initiate systemic steroid treatment (see Section 9.0) Consult Hepatology if not improving within 1 week Resume when symptoms resolve to $\leq$ Grade 1	Omit and initiate systemic steroid treatment (see Section 9.0) Consult Hepatology if not improving within 1 week Resume when symptoms resolve to $\leq$ Grade 1
	Grade 3+ (AST/ALT $>10.0$ x ULN)	Discontinue Consult Hepatology	Discontinue Consult Hepatology
Investigations	Blood bilirubin increased Total bilirubin $>2$ x ULN For patients with Gilbert's syndrome: modify dose only if direct bilirubin is $>2$ x ULN	Discontinue Consult Hepatology	Discontinue Consult Hepatology
Investigations	Lymphocyte count decreased Grade 4	Omit until $\leq$ Grade 2 Resume once $\leq$ Grade 2	Omit until $\leq$ Grade 2 Resume once $\leq$ Grade 2
Renal and urinary disorders	Acute kidney injury Grade 2	Omit until $\leq$ Grade 1 Resume when symptoms resolve to $\leq$ Grade 1	Omit until $\leq$ Grade 1 Resume when symptoms resolve to $\leq$ Grade 1

CTCAE System/Organ/Class (SOC)	ADVERSE EVENTS/SYMPTOMS	ACTIONS	
		Tiragolumab	Atezolizumab
Renal and urinary disorders	Grade $\geq 3$	Discontinue	Discontinue
Respiratory, thoracic and mediastinal disorders	Pneumonitis Grade 2	Omit until $\leq$ Grade 1 Resume once symptoms resolve to $\leq$ Grade 1	Omit until $\leq$ Grade 1 Resume once symptoms resolve to $\leq$ Grade 1
	Grade $\geq 3$	Discontinue	Discontinue
Skin and subcutaneous tissue disorders	Erythema multiforme Grade $\geq 3$	Omit and initiate supportive care per Section 9.0 Refer to Dermatology	Omit and initiate supportive care per Section 9.0 Refer to Dermatology
Skin and subcutaneous tissue disorders	Rash acneiform Grade 2	Continue Initiate supportive care per Section 9.0 Refer to Dermatology if does not improve to $\leq$ Grade 1 within 2 weeks	Continue Initiate supportive care per Section 9.0 Refer to Dermatology if does not improve to $\leq$ Grade 1 within 2 weeks
	Grade 3	Omit and initiate supportive care per Section 9.0 Refer to Dermatology Resume once $\leq$ Grade 1	Omit and initiate supportive care per Section 9.0 Refer to Dermatology Resume once $\leq$ Grade 1
	Grade 4	Omit and initiate supportive care per Section 9.0 Refer to Dermatology Resume once $\leq$ Grade 1	Omit and initiate supportive care per Section 9.0 Refer to Dermatology Resume once $\leq$ Grade 1
Skin and subcutaneous tissue disorders	Rash maculo-papular Grade 2	Continue Initiate supportive care per Section 9.0 Refer to Dermatology if does not improve to $\leq$ Grade 1 within 2 weeks	Continue Initiate supportive care per Section 9.0 Refer to Dermatology if does not improve to $\leq$ Grade 1 within 2 weeks
	Grade 3	Omit and initiate supportive care per Section 9.0 Refer to Dermatology Resume when symptoms resolve to $\leq$ Grade 1	Omit and initiate supportive care per Section 9.0 Refer to Dermatology Resume when symptoms resolve to $\leq$ Grade 1
	Grade 4	Discontinue	Discontinue
Skin and subcutaneous tissue disorders	Stevens-Johnson syndrome $\geq$ Grade 3	Discontinue and initiate supportive care per Section 9.0 Refer to Dermatology	Discontinue and initiate supportive care per Section 9.0 Refer to Dermatology

CTCAE System/Organ/Class (SOC)	ADVERSE EVENTS/SYMPTOMS	ACTIONS	
		Tiragolumab	Atezolizumab
Skin and subcutaneous tissue disorder	Toxic epidermal necrolysis (TEN) Grade 4	Discontinue and initiate supportive care per Section 9.0 Refer to Dermatology	Discontinue and initiate supportive care per Section 9.0 Refer to Dermatology
Skin and subcutaneous tissue disorder	Skin and subcutaneous tissue disorder – Other Drug rash with eosinophilia and systemic symptoms (DRESS)	Discontinue and initiate supportive care per Section 9.0 Refer to Dermatology	Discontinue and initiate supportive care per Section 9.0 Refer to Dermatology
Other Adverse Events	Grade 3	Omit until $\leq$ Grade 1 Resume once symptoms resolve to $\leq$ Grade 1	Omit until $\leq$ Grade 1 Resume once symptoms resolve to $\leq$ Grade 1
	Grade 4	Discontinue	Discontinue

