## 8.0 Dosage Modification Based on Adverse Events

Strictly follow the modifications in this table during neoadjuvant therapy. For adjuvant therapy, these modifications should be regarded as guidelines to produce mild-to-moderate, but not debilitating, side effects. If multiple adverse events are seen, administer dose based on greatest reduction required for any single adverse event observed. Reductions or increases apply to treatment given in the preceding cycle and are based on adverse events observed since the prior dose.

→ **ALERT:** ADR reporting may be required for some adverse events (See Section 10.0) ←

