## 8.3 Adjuvant Dose Modifications Based on Adverse Events (All Arms)

## General guidance:

- a Atezolizumab may be withheld for a longer period of time (i.e., > 12 weeks after event onset) to allow for corticosteroids (if initiated) to be reduced to the equivalent of  $\leq 10$  mg/day oral prednisone. The acceptable length of the extended period of time must be based on the investigator's benefit-risk assessment and in alignment with the protocol requirements for the duration of treatment and documented by the investigator
- b If corticosteroids have been initiated, they must be tapered over  $\geq 1$  month to the equivalent of  $\leq 10$  mg/day oral prednisone before atezolizumab can be resumed
- c Resumption of atezolizumab may be considered in patients who are deriving benefit and have fully recovered from the immune-mediated event. The decision to re-challenge patients with atezolizumab should be based on the investigator's benefit-risk assessment and documented by the investigator

CTCAE System/Organ/Class (SOC)	ADVERSE EVENTS/SYMPTOMS	Atezolizumab
Cardiac disorders	Immune-mediated myocarditis OR Immune-mediated pericardial disorders Grades 2-4	Permanently discontinue atezolizumab
Endocrine disorders	Adrenal insufficiency	See Table 8.31 for management of atezolizumab See Section 9.0 for suggested supportive care
Endocrine disorders	Hyperglycemia	See Table 8.31 for management of atezolizumab See Section 9.0 for suggested supportive care
Endocrine disorder	Hyperthyroidism	See Table 8.31 for management of atezolizumab See Section 9.0 for suggested supportive care
Endocrine disorders	Hypophysitis	See Table 8.31 for management of atezolizumab See Section 9.0 for suggested supportive care
Eye disorders	Eye disorders, other specify: Ocular event, Grade 1	Continue atezolizumab See Section 9.6 for suggested supportive care If symptoms persist, treat as a Grade 2 event
	Eye disorders, other specify: Ocular event Grade 2	Withhold atezolizumab for up to 12 weeks after event onset (a) See Section 9.6 for suggested supportive care If event resolves to Grade 1 or better, resume atezolizumab(b) If event does not resolve to Grade 1 or better while withholding atezolizumab, permanently discontinue atezolizumab (c)
	Eye disorders, other specify: Ocular event Grade 3-4	Permanently discontinue atezolizumab (c) See Section 9.6 for suggested supportive care

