CTCAE System/Organ/Class (SOC)	ADVERSE EVENTS/SYMPTOMS	Atezolizumab
Gastrointestinal Disorders	Diarrhea/Colitis Grade 2	Withhold atezolizumab for up to 12 weeks after event onset (a) See Section 9.0 for suggested supportive care If event resolves to Grade 1 or better, resume atezolizumab (b) If event does not resolve to Grade 1 or better while withholding atezolizumab, permanently discontinue atezolizumab (c)
	Grade 3	Withhold atezolizumab for up to 12 weeks after event onset (a) If event resolves to Grade 1 or better, resume atezolizumab (b) If event does not resolve to Grade 1 or better while withholding atezolizumab, permanently discontinue atezolizumab (c)
	Grade 4	Permanently discontinue atezolizumab
Gastrointestinal disorders	Pancreatitis (immune-mediated) Grade 2 or 3	Withhold atezolizumab for up to 12 weeks after event onset (a) If event resolves to Grade 1 or better, resume atezolizumab (b) If event does not resolve to Grade 1 or better while withholding atezolizumab, permanently discontinue atezolizumab (c) For recurrent events, permanently discontinue atezolizumab (See Investigations/Lipase increased or serum amylase increased below)
	Grade 4	Permanently discontinue atezolizumab
General disorders and administration site conditions	Infusion-related reaction Grade 3-4	Discontinue
Infections and infestations	Myelitis, immune-mediated Grade 2-4	Permanently discontinue atezolizumab See Section 9.0 for suggested supportive care
Immune system disorders	Allergic reaction or Anaphylaxis Grade 2	Hold and resume when symptoms resolve to ≤Grade 1 Pre-treatment required prior to subsequent doses (Section 9.0)
	Grade 3-4	Discontinue
Immune system disorders	Immune system disorders, other (specify): Immune-related myasthenic syndrome/myasthenia gravis, Guillain-Barré, or meningoencephalitis	Permanently discontinue atezolizumab

CTCAE System/Organ/Class (SOC)	ADVERSE EVENTS/SYMPTOMS	Atezolizumab
Investigations For patients without hepatocellular carcinoma (HCC)	Aspartate aminotransferase increased or Alanine aminotransferase increased or Blood bilirubin increased Grade 1	Continue, and monitor LFTs more frequently until return to baseline values

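### Arm C's binding dose table omits immune-mediated myelitis from its permanent-stop row, so Grade 3 restarts both drugs and Grade 2 requires no action, while the adjuvant table stops atezolizumab at Grades 2-4

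*Combined protocol and SAP*

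**What the plan says.** Section 8.0 gives the two phases different force. Before surgery: "Strictly follow the modifications in this table during neoadjuvant therapy". After surgery: "For adjuvant therapy, these modifications should be regarded as guidelines". It also ties each dose decision to events seen since the last dose.

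Table 8.22 (Arm C, neoadjuvant) has one row for immune-related myasthenia, Guillain-Barré syndrome and meningoencephalitis. Its tiragolumab cell reads "Permanently discontinue tiragolumab", and the atezolizumab cell matches. Myelitis appears nowhere in the table. The catch-all row for other Grade 3 events says, for both drugs, to hold and then "Resume once symptoms resolve to $\leq$ Grade 1". The catch-all Grade 4 row discontinues both, and there is no catch-all row for Grade 2. The only cardiac row covers any clinically symptomatic disorder: "Omit until myocarditis is ruled out by Cardiology".

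Table 8.3 (adjuvant) has a row headed "Myelitis, immune-mediated" for Grades 2-4, and a row for immune-mediated myocarditis or pericardial disorders at Grades 2-4. The action in both is "Permanently discontinue atezolizumab". Neither carries the letter for note (c), which reads "Resumption of atezolizumab may be considered in patients who are deriving benefit and have fully recovered from the immune-mediated event".

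Section 7.3 offers adjuvant atezolizumab, up to 8 cycles, to completely resected patients in all arms and sets no condition on earlier toxicity.

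**The concern.** For myelitis, the table that sites must follow gives the looser instruction, and gives it while two checkpoint inhibitors are being infused together. The table that is only advisory, for one drug, gives the strict one. Section 10.561 names myelitis, myocarditis and pericarditis among the events of special interest for these drugs, so the sponsor already recognises the risk. The omission looks like a missing entry in a row that already covers the neighbouring neurologic events, not a deliberate choice.

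What is at stake is patient safety. A site that follows the protocol exactly could restart both drugs after Grade 3 myelitis, or continue them through Grade 2 myelitis. It could then start adjuvant atezolizumab after surgery without meeting an explicit bar.

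**Working it through.** The plan states no figure on this point, so the check is a comparison of the tables, then of the rules that might fill the gap.

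**Step 1. The two tables side by side.**

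| Event | 8.22, Arm C (strict), both drugs | 8.3, adjuvant (guideline), atezolizumab | Result |
|---|---|---|---|
| Myelitis, Grade 2 | No row, so no action required | Permanent stop, no note (c) | Conflict |
| Myelitis, Grade 3 | Catch-all: hold, restart at Grade 1 or better | Permanent stop, no note (c) | Direct conflict |
| Myelitis, Grade 4 | Catch-all: discontinue | Permanent stop | No conflict |
| Confirmed myocarditis | Hold whose end condition is never met; no stop worded | Permanent stop at Grades 2-4 | Missing wording |
| Pericardial disorder, Grades 2-3, myocarditis ruled out | Cardiac hold ends; no permanent stop | Permanent stop | Missing stop |

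Grade 4 cardiac events are discontinued only if the catch-all Grade 4 row is read to cover them. The cardiac row itself does not say so.

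**Step 2. Rules that might close the gap before surgery.**

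- Section 9.69b prescribes steroids for Grade 2 myelitis but says nothing about dosing. For Grades 3-4 it refers to a neurologist and institutional practice.
- Section 8.2 lets a provider hold for a troublesome Grade 2 event after discussion with the principal investigator. This is permitted, not required.
- Section 8.13 requires a steroid taper of at least one month before atezolizumab resumes, once a drug is held and steroids are started.
- Section 8.2 sends the patient to surgery once all drugs have been omitted for more than 28 days. With the taper, a held event treated with steroids will usually end the neoadjuvant course.
- For pericardial disorders, 9.69a2 holds atezolizumab at Grade 1, and 9.69a3 gives steroids and a taper of more than a month at Grades 2-4. Neither words a permanent stop.

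Neoadjuvant re-dosing is therefore open in two situations: Grade 2 myelitis that nobody holds, or Grade 3 myelitis that resolves within 28 days without steroids. After a cycle 1 event the maximum is 4 - 1 = 3 further doses of each drug.

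**Step 3. Carry-over to the adjuvant phase.** When a drug is held until surgery, the last neoadjuvant dose is the prior dose. The event then lies inside the 8.0 look-back for the first adjuvant dose. Section 9.51 also directs retreatment decisions to Sections 8.2-8.3. Both lead to Table 8.3 and its permanent stop, but with the force of guidance. If dosing was continued or restarted, an event that resolved before the last dose falls outside the look-back.

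The 105-day rule in 8.13 need not intervene. A 28-day omission plus the schema's surgical period of about 4-6 weeks is 28 + 28 = 56 to 28 + 42 = 70 days, and beyond 105 days the investigator may still resume.

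**Step 4. Frequency, by assumption only.** Section 16.1112 plans 32 treated patients; the 4 extra enrolments in 16.132 replace patients who never start. With an assumed per-patient rate p for one event type, expected cases are 32p and the chance of at least one is 1 - (1 - p)^32:

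- p = 0.1%: 0.03 cases, 3.2%
- p = 0.5%: 0.16 cases, 14.8%
- p = 1%: 0.32 cases, 27.5%

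The only rate in the documents (15.17, below 1% with atezolizumab) covers myocarditis and pericardial disorders, not myelitis and not the combination. It is not limited to the affected grades or to 12 weeks of treatment. The range therefore overstates the cases that this gap would reach.

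**The case against.** The strongest reply is that existing rules already prevent most of the harm. Much of it stands.

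- **Cardiac.** A reader might infer that patients with confirmed myocarditis would be re-dosed before surgery. The text does not support that, because the hold ends only when myocarditis is excluded. For pericardial Grades 2-3, the steroid taper and the 28-day rule lead to surgery. Only the wording of a permanent stop is missing.
- **Adjuvant exposure.** A reader might infer that up to 8 adjuvant doses would follow because nothing stands in the way. After a held event, the 8.0 look-back and 9.51 do point to Table 8.3. What survives is that this is guidance, while 7.3 has no bar.
- **Strict against advisory.** Section 9.51 calls both 8.2 and 8.3 guidelines, which softens the contrast. Section 8.0 still says strictly for the neoadjuvant table, so the contrast is weakened but not removed.
- **Follow-up route.** Section 13.17 sends patients who stop neoadjuvant treatment for other medical conditions to survival follow-up. Whether that includes toxicity is arguable, and 8.2 and 13.12 provide for surgery after toxicity.
- **General laxity.** A reader might infer that Table 8.22 is looser than 8.3 throughout. It is not. For Grade 2 hyperthyroidism, 8.22 requires a hold, while the adjuvant guidance in 8.31 only asks the site to consider one.

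None of this answers the myelitis conflict at Grade 3, or the absence of any required action at Grade 2.

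**Conclusion.** The point holds for immune-mediated myelitis at Grades 2 and 3. The binding Arm C table either requires nothing or instructs a restart of both drugs, where the protocol's own adjuvant table stops atezolizumab permanently with no re-challenge note. Grade 4 is not in conflict. The cardiac omission is secondary: an explicit permanent stop is missing, with little prospect of re-dosing before surgery. The adjuvant carry-over is covered by guidance but not by a rule.

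The consequence would be serious for the patient affected, but such patients should be few. No probability can be drawn from the documents for myelitis, and the range above is an assumption that errs high. The conclusion rests on two readings: that an unlisted event goes to the catch-all row, and that the letter (c) applies only to rows that carry it. Sample size, the pCR estimate and its analysis set are unaffected.

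**What to change.** Three edits:

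1. Add immune-mediated myelitis, Grades 2-4, to the neurologic permanent-discontinuation row of Table 8.22 for both drugs. Make the same addition to the matching atezolizumab cell of Table 8.21 for consistency, although Arms A and B are closed to enrolment.
2. Keep the cardiac hold in Table 8.22 for suspected cases, and add: if immune-mediated myocarditis or a pericardial disorder of Grade 2-4 is confirmed, permanently discontinue both drugs.
3. Add one sentence to 7.3: a patient who had one of these three events in the neoadjuvant phase does not start adjuvant atezolizumab and, if rendered NED, enters observation. This mirrors 13.32 and uses the 3-monthly schedule in footnote 29 of 4.2. It also supplies a route that 13.2 does not give, since 13.2 covers only patients not rendered NED and those who refuse adjuvant treatment.

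The bar should not extend to every event that Table 8.3 stops without note (c). That would add, for example, Grade 4 colitis or pancreatitis, Grade 3-4 kidney injury and Grade 3-4 infusion reactions, which raise separate questions and costs.

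The cost is a few table entries and one sentence. A rare patient forgoes adjuvant atezolizumab and falls outside the RFS analysis set, which 16.12 limits to patients who began adjuvant treatment.
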